# Lay Abstract

Human milk is the ideal source of nutrition for all infants. When parent milk is unavailable, pasteurized human donor milk as a supplement versus formula, reduces the risk of necrotizing enterocolitis, a severe bowel emergency in very preterm infants. Donor milk use in well-baby units is a growing practice despite a lack of scientific evidence for its benefit or an understanding of associated cost. In Canada, where lactation support is readily available in most well-baby units, 35-50% of newborns are supplemented with formula prior to hospital discharge. To date, there is no trial to study the impact on breastfeeding and health outcomes following donor milk versus formula supplementation in the well-baby nursery. We aim to conduct a randomized controlled trial to test whether supplementation with donor milk compared to formula for infants during initial hospital stay increases exclusivity and duration of human milk feeding at 4 months, an important determinant of public health. We will also study the impact of type of supplementation on measures of newborn health, growth, behavior, feeding efficacy, parental stress, and use of informally shared milk. The financial implications of each type of supplementation will also be considered. Our findings will provide evidence-based guidelines for feeding Canadian newborns with potential long term implications for child and family health and well-being.

# Abbreviations

BSES-SF, Breastfeeding Self-Efficacy Scale – Short Form; CanDo, Canadian Donor Milk; IFI, Infant Feeding Intentions; NICU, Neonatal Intensive Care Unit; RCT, Randomized Controlled Trial; SGA, Small for Gestational Age; STAI, The State-Trait Anxiety Inventory; VLBW, Very Low Birth Weight; WHO, World Health Organization

#### **1.1 Project Summary**

**Background and Importance**: Human milk is the ideal nutrition for all infants, and research has demonstrated that human donor milk can provide health benefits for preterm infants. Approximately 35-50% of late preterm and term infants admitted to a well-baby unit after birth require supplementation due to various reasons including hypoglycemia, weight loss, or insufficient availability of parent's milk. However, there is limited research to guide decision making on which supplement to prescribe. Despite this, many hospitals are introducing donor milk in well-baby units in light of the growing recognition of the health protective effects of human milk.

**Goals/ Research Aims**: The primary research aim of this study is to compare the effects of supplementing parent's milk with donor milk versus formula in infants at increased risk for supplementation (infant born to a mother with diabetes, infant with a birth weight smaller than expected for the gestational age (SGA)) on exclusive human milk feeding at 4 months of age. Secondary research aims include: examining the effects of supplementing parent's milk with donor milk on any or exclusive human milk feeding rates at 1, 2 and 3 months, infant health and growth at hospital discharge and at 1, 2, 3, and 4 months, and breast feeding self-efficacy scores. Exploratory outcomes include: infant temperament scores at 1, 2, 3, and 4 months, and parental mental health scores at 2 and 4 months using validated questionaires, milk cortisol concentrations at 2 and 4 months, the use of informally shared milk, and the associated financial costs of a donor milk program versus formula.

**Methods/ Approaches/ Expertise**: This proposed study is a randomized, controlled, singlecenter trial that will involve assigning participants to two intervention arms (n=56 infants/arm). The intervention will involve providing donor milk or formula in bottles and will last for the duration of the infant's initial hospitalization, followed by monthly phone calls and a virtual or inperson assessment at 4 months. At each time-point of 1, 2, 3, and 4-month, surveys of breast feeding self-efficacy, and health and infant temparement will be conducted, and the infant's anthropometrics will be measured. Additionally, measures of parental depression, anxiety and stress will be assessed with survey-based tools at 2 and 4 months. A coincident human milk sample will be collected at 2 and 4 months and will be analysed for cortisol concentrations. The research team has experience running feeding interventions and donor milk trials in newborns, and includes experts in nursing, medicine, dietetics, and milk banking. **Expected Outcomes**: This proposed research holds the potential to make a meaningful impact on public health. In Canada, with approximately 350,000 level I nursery admissions each year and high rates of formula supplementation ranging from 35-50%, there is a clear opportunity for improvement. By promoting exclusive human milk feeding, exploring evidence-based practices to inform hospital guidelines, and reducing the reliance on informal milk sharing, this research aims to enhance the health outcomes for both parents and infants. Additionally, it seeks to deepen our understanding of early parent-child interactions, fostering greater awareness and knowledge in this area.

#### 1.2 Research Background

For this proposed research, human milk refers to the totality of parent milk and donor milk. Parent milk is a gender inclusive term used for planning future research whereas mother's milk is used where describing reports from the literature where gender is not further specified. Donor milk refers to pasteurized human donor milk from an accredited milk bank.

Newborns are typically fed via parent milk as the primary source of nutrition and the multitude of benefits of mother's milk are summarized in the 2016 Lancet breastfeeding series (1). According to the recent 2023 Lancet breastfeeding report (2), although breastfeeding has been proven to have health benefits for mothers and infants in both high-income and low-income settings, less than 50% of infants worldwide are being breastfeed in accordance with the World Health Organization's (WHO) recommendations. This is due to a variety of factors, including societal, political, and economic influences (3, 4).

When a supplement to parent milk is required in the newborn period, it is uncertain whether this should be formula or donor milk as the former is associated with a reduction in exclusive human milk feeding later in infancy while the latter caries elevated financial cost and inequitable distribution within Canada and globally (5, 6). The impact of using donor milk versus formula as a supplement during initial hospitalization on adherence to breastfeeding guidelines post-discharge is unknown. There are more than 350,000 (7) infants born annually in Canada of whom approximately 90% are admitted to well-baby units with many hospitals reporting a typical formula or donor milk supplementation rate of about 35-50%, particularly for high risk infants (6). The reasons for supplemental feeds include hypoglycemia, hyperbilirubinemia, weight loss, insufficient volume of parent's milk, surrogacy, parental preference or for unknown reasons.

Historically, formula has been the predominant supplement when one is required for any infant; however, as human milk banking has grown rapidly, the interest in and the practice of providing donor milk to infants in a well-baby unit has increased (8-10). Health Canada and WHO recommend exclusive breastfeeding for the first 6 months for all infants (11, 12). The WHO goes on to state that if mother's milk is unavailable or insufficient in volume, both preterm and healthy term infants should be fed donor milk. The use of donor milk in populations other than very low birth weight (VLBW) infants, however, has not been systematically investigated. A recent systematic scoping review of donor milk in populations other than preterm infants concluded that current evidence is limited by the lack of randomized trials as well as direct health measures and recommended further research be conducted (13). One retrospective study compared infants admitted to a well-baby unit in Florida before (n=73) and after (n=49) the commencement of a donor milk program (14). Approximately half of the infants' families were called 6 months post hospital discharge and asked about feeding practices. The rate of exclusive breastfeeding to >6 months had increased from 15% to 58% (adjusted odds ratio=5.13, 95% confidence interval 1.37, 19.23, p=0.015).

A recent pilot study in California investigated the feasibility of use of donor milk versus formula in 32 term and late preterm infants admitted to neonatal intensive care unit (NICU). The consent rate was 52%, and breastfeeding attempts increased significantly over time in the donor milk group compared to the formula group. Growth at multiple time points was similar between the two groups (15). The results of the study confirmed that randomly assigning term and late preterm infants into donor milk or formula groups when their mother's milk is not available is feasible, and that donor milk may increase breastfeeding attempts without having a negative effect on growth and appropriate weight gain.

Few data are available regarding the use of donor milk in Canadian well-baby units, although at least 5 hospitals in Ontario are presently doing so (personal communication to the Rogers Hixon Ontario Human Milk Bank). Among 214 American hospitals surveyed in 2017, the prevalence of donor milk use in well-baby units was 17.6% with the majority (85%) of donor milk programs in these hospitals having started in the previous 5 years (10). In 2018, a survey of American hospitals participating in the Better Outcomes through Research for Newborns Network, showed that of 71 hospitals responding, 28% offered donor milk routinely when a supplement was required and 40% had donor milk available in the well-baby unit (9). A 2018 survey of hospitals in Massachusetts served by a single milk bank (n=51 respondents), showed that 43% of hospitals with access to donor milk use it routinely in their well-baby unit (8). A further concern is

the growing use of informally shared milk (donor milk that is sourced other than from a milk bank and is typically not pasteurized) to meet supplementation needs. Both Health Canada and the Canadian Paediatric Society have issued warnings about this practice (16, 17).

In view of limited high-quality evidence, adequately powered trials that evaluate the impact of donor milk compared to infant formula as a supplement to parent milk in well-baby units are needed; we thus propose to conduct a randomized controlled trial (RCT) to investigate whether prescribed supplementation with donor milk compared to formula for infants at higher risk of supplementation during initial hospitalization impacts exclusive human milk feeding at 4 months of age. We will also study the impact of types of supplementation on measures of newborn health, growth, and temperament, feeding efficacy, parental stress, use of informally shared milk and the financial costs of donor milk versus formula supplementation.

# 1.3 Goals/ Research Objectives

#### 1.3.1 Primary research objective:

To determine whether the provision of donor milk as prescribed as a supplement to parent's milk for infants at higher risk for supplementation and admitted to a well-baby unit improves exclusive human milk feeding at 4 months of age compared to supplementation with formula.

#### 1.3.2 Secondary research objectives:

To explore whether the provision of donor milk as a supplement to parent's milk affects any, or exclusive, human milk feeding rates at 1, 2, and 3 months of age, breast feeding self-efficacy scores at 1, 2, 3 and 4 months, infant health and growth at hospital discharge and at 1, 2, 3, and 4 months, and percent weight loss, glucose levels, length of hospital stay at hospital discharge.

#### 1.3.3 Exploratory outcomes:

To explore whether the provision of donor milk as a supplement to parent's milk affects infant temperament scores at 1, 2, 3 and 4 months, and parental stress, anxiety and depression scores at 2 and 4 months using validated questionnaires. To also explore milk cortisol levels at 2 and 4 months and the prevalence of informally shared milk after hospital discharge. An economic evaluation of the donor milk program versus formula will also be conducted concurrently.

# 1.4 Rationale and Significance

The proposed trial will be the first randomized controlled trial that will evaluate the type of nutritional supplementation provided in the immediate newborn period to infants during their initial hospitalization in a well-baby unit. Although the goal is for exclusive human milk feedings from birth, up to 50% of all infants in a well-baby unit receive supplementation. The current standard is for this supplement to be a bovine milk formula. However, the practice of using human donor milk for this population is increasingly growing without any research evidence. With approximately 350,000 level I nursery admissions per year in Canada and a supplementation rate of approximately 35-50% in higher risk infants, this proposed research can have far-reaching public health implications. This may include improved health outcomes for parents and infants by improving exclusive human milk feeding and deepening our understanding of early parent-child interactions, while improving evidence-based practices. Further, this study has the potential to result in risk reduction by reducing the occurrence of informal human milk sharing.

# 1.5 The novelty of the approach

To date, the limited published evidence supporting the use of donor milk is in the form of prepost implementation reports. We propose the first RCT to study the potential health impact of donor milk use in the well-baby unit. Our proposed research takes a holistic approach with the primary outcome (exclusive breastfeeding) being an important determinant of public health. The exploratory measures assess a wide range of parent-child interactions including measures of infant temperament and parent mental health. These outcomes are increasingly being recognized as critical in early infant development and family well-being and will be evaluated as potential outcome variables for future research. Human milk cortisol levels will be analyzed to further study the potential biological underpinnings of the link between parental stress and infant health.

# 1.6 Trial design

The proposed pragmatic RCT will have 2 arms (open label donor milk/formula supplement, n=56 infants/arm); to assess how awareness of donor milk supplementation impacts feeding and other related outcomes. Families will be recruited upon admission to the well-baby unit and their infant registered for the trial only if a feeding supplement is prescribed. The intervention will last for the duration of the hospitalization and the primary outcome, exclusive human milk feeding, will be assessed at 4 months via an in person or virtual visit, according to the family's wishes and to maximize patient retention.

#### 1.6.1 Inclusion criteria:

Infants admitted to the well-baby unit at Sinai Health whose parent(s) intend to feed parent milk and who require supplementation:

- Infants of gestational/ type 1/ type 2 diabetic mothers
- Infants who are born small for gestational age (SGA) by using a sex-specific reference population and determining if their birth weight falls below the 10th percentile for gestational age
- Infants with a birth weight less than 2.5 kg

Note: Families will be approached according to the above stated criteria however only registered for trial participation if consent is secured and the infant require supplementation.

#### 1.6.2 Exclusion criteria:

Enrollment in any other clinical study affecting nutritional management during the feeding intervention; anticipated change in primary caregiver (person providing the feed) prior to 4 months; refusal to consent to donor milk; supplementation with formula prior to enrollment; any physical condition that may impact growth (ex: skeletal dysplasia).

#### 1.6.3 Guidelines for feeding during the intervention phase

The randomization occur once trial registration occurs. The intervention will continue throughout the hospitalization at any time that a supplementation is recommended by the clinical team, and is expected to last from 0 to 72 hours post-birth.

All donor milk will be aliquoted into individualized containers in the Rogers Hixon Ontario Human Milk Bank which is located in Sinai Health. The containers for study groups 1 and 2 will be open labelled and will be named as "CanDo trial-donor milk" and "CanDo trial-formula". The decision regarding the timing and duration of the supplementation will be determined by the medical team in the well-baby unit based on the specific needs and circumstances of each mother-infant dyad. As this study follows a pragmatic approach, the clinical team will assess the need for supplementation based on the mother-infant dyad's condition. General feeding guidelines, including ad lib/ on-demand parent milk feeding as per the parent's plans, will be in place. The management of hypoglycemia will be according to the recommendations of the Canadian Paediatric Society and in accordance with Mount Sinai's hypoglcemia protocol including routine glucose monitoring for all children born <37 weeks gestation, <10% birth weight for gestation, <2.5 kg or >4.5 kg birth weight, with a supplement provided (dextrose gel followed by supplemental feed) for any glucose <2.6 mmol/L in the first 72 hours after birth (18).

#### 1.6.4 Practical arrangements for allocating participants to trial groups

Families will be invited to participate in the trial during their antenatal visits to the diabetes and placenta clinics. If they agree to participate, they will be asked to sign the consent form. After giving birth, upon admission to the well-baby unit they will be approached again for confirmation of their willingness to participate in the trial and to add infant's name to the consent form. Infants who are prescribed a supplement will be entered into the trial and randomly assigned to either the donor milk or formula group. Prior to the start of the study, a unique randomization schedule will be generated. The computer-generated randomization schedule will be securely stored in a sealed binder, with each participant's allocation placed in separate envelopes. These envelopes will be securely held in a locked procedure room, either within the well-baby unit. Importantly, to maintain blinding, the study coordinator will access the randomization schedule one envelope at a time during participant enrollment and allocation. This approach ensures that the study coordinator cannot see whether a participant will receive donor milk or formula until the point of assignment. The study allocation will be randomly assigned in a 1:1 ratio, using random blocks of 2 or 4. Furthermore, to prevent potential bias and uphold the integrity of the randomization process, the randomization schedule will incorporate stratification factors. These factors include whether the infant was born to a diabetic mother, whether they are small for gestational age, and the infant's sex. Stratification will facilitate the equitable distribution of supplementation rates across these distinct groups, thereby contributing to the robustness of the randomization process.

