#### 1.6.5. Communication of group allocation with the nursing staff and parent(s):

The responsibility for communicating group allocation lies with the study coordinator. Following the completion of the randomization process, parents and nursing staff will be informed of the group allocation, as the study is open-label, and this information aligns with the study design. During this discussion, parents will receive a clear explanation of their infants' group assignment, including its implications and details regarding the associated supplementation. It will also emphasize the voluntary nature of participation and the option for parents to withdraw from the study at any point.

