#### 1.13.1 Survey Data Using REDCap:

Data collected during the study will be securely managed using the REDCap platform hosted on the University of Toronto's server. This setup ensures robust security during data collection. After completing data collection, all information will be securely transferred to the Mount Sinai Hospital server for storage, maintaining the highest level of data security and confidentiality.

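### Small block sizes stated in the protocol, with on-unit envelopes opened by the coordinator who announces every arm, leave allocations predictable and the trial vulnerable to selection bias

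*Protocol*

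**What the plan says.** Section 1.6.4 sets the allocation method: "The study allocation will be randomly assigned in a 1:1 ratio, using random blocks of 2 or 4". The schedule is stratified: "These factors include whether the infant was born to a diabetic mother, whether they are small for gestational age, and the infant's sex". Allocations sit in separate envelopes kept at the unit: "These envelopes will be securely held in a locked procedure room, either within the well-baby unit" (the second location implied by the word either is not given). Access is described as follows: "the study coordinator will access the randomization schedule one envelope at a time during participant enrollment and allocation". The protocol draws this assurance from the arrangement: "This approach ensures that the study coordinator cannot see whether a participant will receive donor milk or formula until the point of assignment".

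Section 1.6.5 makes the coordinator responsible for disclosing the arm, and "parents and nursing staff will be informed of the group allocation, as the study is open-label". The project summary (1.1) describes one centre. Section 1.17 places the coordinator on the Steering Committee.

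On entry, section 1.6.4 has families consent antenatally and confirm willingness on admission after birth. Infants are randomised only once a supplement is prescribed. Section 1.6.3 leaves that judgement to clinicians: "The decision regarding the timing and duration of the supplementation will be determined by the medical team". No section withholds the block sizes from the coordinator or unit staff, and none describes allocation from outside the unit.

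**The concern.** Sealed envelopes opened one at a time prevent someone from looking up the next arm. They do not prevent someone from working it out. In an open-label trial at one site, the person opening the envelopes knows every past arm. With the block sizes known and as small as 2, that history often points strongly to the next arm.

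A prediction matters only if something about entry can still change. Two steps come before randomisation: willingness is confirmed again after birth, and a clinician decides that a supplement is needed. Section 1.6.2 also excludes infants given formula before enrolment, so a consented infant can drop out of eligibility between consent and registration. Infants lost at these points are never randomised, so the intention-to-treat analysis in 1.9.1 cannot recover them.

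The primary outcome is parent-reported exclusive human milk feeding at 4 months, which plausibly depends on parental motivation. The adjusted models in 1.9.1 include only risk condition and sex. If parents' motivation influenced who entered when a given arm was expected, the arms would differ on it and the planned adjustment would not remove the difference.

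**Working it through.** The protocol gives no predictability figure to reproduce.

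**Inputs from the protocol.** Ratio 1:1 and blocks of 2 or 4 (1.6.4). Three binary stratification factors give 2 × 2 × 2 = 8 strata (1.6.4). Total 112 infants (1.8: 47/0.85 = 55.3, rounded up to 56 per arm).

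**Assumptions.** The mix of block sizes is not stated, so I take 50:50 and vary it. Stratum shares are not stated, so I take diabetic mother only 50%, SGA only 30%, both 5%, neither 15% (possible through the birth-weight criterion), each split evenly by sex. The observer knows the block sizes and the past arms in the stratum but not where blocks begin or end, and updates by Bayes' rule. The separate twin plan (blocks of two, described under Table 2) is left out. There, the second twin's arm is fixed by design.

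**Exact check, one long sequence, equal mix.** Take one block of 2 and one of 4, six allocations in all, and count those made while the arms are unequal.
- Block of 2: the second allocation, so 1.
- Block of 4: the second (always), the third (only if the first two match, probability 1/3) and the fourth (always), so 1 + 1/3 + 1 = 7/3.
- Share made with unequal arms: (1 + 7/3)/6 = 55.6%.
- Correct guesses of the lagging arm among these: block of 2 gives 1; block of 4 gives 2/3 + 1/3 + 1 = 2; total 3. Accuracy 3/(10/3) = 90%.
- The other 6 − 10/3 = 8/3 allocations are a coin toss. Overall correct: (3 + 4/3)/6 = 72.2%, against 50% under simple randomisation.

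**Why the mix matters.** After the first allocation of a known new block, the probability that the next is the other arm is
- equal mix: 1/2 × 1 + 1/2 × 2/3 = 83.3%;
- blocks of 4 outnumbering 2 by 2:1: 1/3 × 1 + 2/3 × 2/3 = 77.8%.

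The second figure is below 80%, so the share above that threshold drops when blocks of 4 dominate.

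**Simulation, 112 infants in 8 strata, incomplete last blocks included.**

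| Scheme (mix) | Correct | ≥75% predictable | ≥80% predictable | Certain |
|---|---|---|---|---|
| 2/4 (equal) | 71% | 53% | 53% | 10% |
| 2/4 (1:2, more 4s) | 70% | 54% | 43% | 12% |
| 2/4 (2:1, more 2s) | 72% | 52% | 52% | 8% |
| 4/6/8 (equal) | 66–67% | 35–38% | 18–19% | 2% |

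Ranges reflect separate runs, including one with equal stratum shares. An observer who tracks only the overall running difference, ignoring strata, is right about 58% of the time with 2/4 blocks.

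**Balance, 2/4 against 4/6/8 (equal mixes).** Mean absolute overall imbalance is about 1.8 against 2.4 infants (95th percentile 4 against 6). Absolute imbalance summed over the eight strata is about 4.8 against 6.6 (95th percentile 8 against 10).

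**The case against.** **The observer is close to a worst case.** This stands in part. Tracking eight strata separately takes effort. At the 2–3 infants per week in section 1.10, an average stratum receives one infant every 8/3 to 8/2 weeks, or about 3 to 4 weeks. Section 1.6.5 says nursing staff are told allocations, but not that they keep a history by stratum. The coordinator plausibly fits the model. Prescribing staff fit it much less well, and the 58% figure is nearer their position.

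**Over half of allocations being highly predictable is not a fixed property of the design.** This stands. A reader might infer it from the equal-mix result, but the protocol gives no mix, and at the 80% threshold the share falls to 43% if blocks of 4 dominate 2:1. Predictable also does not mean certain: about 10% of allocations are certain when block boundaries are unknown.

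**The order of events protects the trial.** It narrows the opportunity. Consent is signed before birth, and so before birth weight settles SGA status. Another infant in the same stratum may be allocated between confirmation and prescription, and part of the entry trigger is a glucose threshold (1.6.3). But confirmation after birth and a discretionary decision to supplement both precede randomisation, so the opportunity stays open. A reader might also assume that the coordinator is the one who re-confirms consent. Section 1.6.4 does not say who does.

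**Motivation is measured and partly restricted.** All entrants must intend to feed parent milk (1.6.1), and feeding intention is scored at baseline (1.7). That would let an imbalance be seen, but the planned models do not adjust for it.

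**Conclusion.** The concern holds as a weakness in allocation concealment. The assurance in section 1.6.4 covers seeing the next arm, not inferring it. With blocks of 2 or 4 known and arms tracked within stratum, about 70–72% of allocations can be guessed across the block mixes tried. The share that is at least 80% predictable is 53% under an equal mix, and 43% if blocks of 4 outnumber blocks of 2 by 2:1. These figures rest on the unstated block mix, the assumed stratum shares and an attentive observer. That the coordinator knows the block sizes is an inference, supported by their presence in the protocol and by the coordinator's Steering Committee seat.

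A reader might go further and infer that the primary comparison will be biased. The documents do not support that: nothing shows that anyone would act on a guess, and no effect on the primary outcome can be quantified from them. The point is an avoidable vulnerability with a cheap remedy, and the sponsor should address it.

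**What to change.** 1. Have each allocation released from outside the unit, only after consent is confirmed and the infant is registered. The current text already places registration after consent and randomisation after registration, so what changes is who holds the list. It could be a person outside the unit. It could also be the data-capture system in section 1.13.1 ("Data collected during the study will be securely managed using the REDCap platform"), if its randomisation function is available; the protocol describes that system for data collection only.
2. Move the block sizes into a document withheld from recruiting and unit staff.
3. Drop the block size of 2 and use randomly varying larger blocks, for example 4, 6 and 8, within the same strata.

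Steps 1 and 2 are the essential ones. Larger blocks alone lower correct guesses only from about 71% to 66%, although the share at least 80% predictable falls from 53% to about 19%.

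The cost is a new list and a wording change in 1.6.4. If recruitment has begun, the change can apply to the remaining allocations. The statistical price is the added imbalance shown above: about 0.6 infants overall and 1.8 summed within strata, out of 112. The within-stratum rise deserves mention because 1.9.3 plans subgroup analyses by risk condition and sex, but it is modest.
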